2. OBJECTIVES & OUTCOME MEASURES / ENDPOINTS

OVERALL AIM

The overall aim is to conduct a two-arm multicentre, rater-blind, randomised controlled trial comparing CBT_{BAR} plus TAU vs. TAU only for BAR individuals to evaluate the efficacy of a specific intervention (CBT_{BAR}). We also aim to investigate how CBT_{BAR} impacts on the pathway between key psychological processes and mood swings. The overarching research questions are:

- 1) To what extent is CBT_{BAR} (a psychological therapy) effective in reducing distressing mood swings when compared to Treatment As Usual (TAU) for BAR individuals? (*Measured at 27-weeks follow-up*)
- 2) Investigate how CBT_{BAR} impacts on the pathway between key psychological processes and mood swings measured at 17-week follow-up.
- 3) What are the perceptions of patients and health care professionals regarding the implementation of this therapy in NHS services?

EFFICACY AIMS

The trial has a number of efficacy aims:

- 1) To determine the efficacy of CBT_{BAR} (a specifically developed psychological therapy) in reducing distressing high and low mood swings when delivered to patients meeting BAR criteria.
- 2) To determine whether positive effects of CBT_{BAR} last over a 52-week follow-up period.
- 3) To investigate patients', health care professionals, and NHS stakeholders' perceptions of implementation of CBT_{BAR}.

Primary Objective

To determine the efficacy of CBT_{BAR} (a specifically developed psychological therapy) in reducing distressing high and low mood swings when delivered to participants meeting BAR criteria.

Primary Outcome Measure/Endpoint

Mood swing symptom severity assessed by SCID-5 + PSR's (SCID LIFE) [1] at 27-week (post treatment) as measured by the PSR scores as an average of the prior 4 weeks. A longitudinal severity rating of overall symptom levels for each week over the time period (prior 4 weeks) is completed providing two LIFE scores, one for mania and one for depression [1].

Mechanism Objective

To investigate the extent to which CBT_{BAR} impacts on distressing high and low mood swings (SCID-5 + PSR's (SCID LIFE)) via extreme positive and negative appraisals of internal states (HAPPI) which then impacts on subsequent behaviours (BC) used to control mood (ISS).

Mechanism Measures/Endpoint

- 17-week (during therapy): Hypomanic Positive Predictions Inventory (HAPPI), the Behaviour Checklist (BC) and Internal States Scale (ISS)

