Health Utility, measured at 27-, and 52-week follow-up points:

- Service Use Interview (adapted for this study): use of formal and informal health and social care at 27and 52-week follow-up.
- Health Questionnaire (EQ-5D-5L; [69]): health status and health related utility scores of participants at 27- and 52-week follow-up.
- Recovering Quality of Life (ReQoL; [70]):

Functioning, measured at 27-, and 52- week follow-up points:

- Global Assessment of Functioning scale (GAF; [71]): measure of an individual's level of social, occupation and psychological functioning at 27- and 52-week follow-up.
- Social and Occupational Functioning Assessment Scale (SOFAS; [72]):_Additional measure of an individual's level of social & occupational functioning at 27- and 52-week follow-up.
- World Health Organisation Quality of Life (WHOQOL-BREF; [73]): will be administered to assess quality of life.

Additional secondary outcomes, measured at 27-, and 52- week follow-up points:

- Pittsburgh Sleep Quality Inventory (PSQI; [74]): Measure quality of sleep at the 27- and 52-week followup.
- Positive and Negative Sleep Appraisal Measure (PANSAM;[75]): Measure appraisals of sleep across high and low mood states at the 27- and 52-week follow-up.
- Metacognition Questionnaire (MCQ-30;[76]): at 27- and 52-week follow-up
- Desire Thinking Questionnaire (DTQ; [77]): at 27- and 52-week follow-up
- Response Style Questionnaire (RSQ; [78]): at 27- and 52-week follow-up
- Brief Core Schema Scale (BCSS; [79]): at 27- and 52-week follow-up
- All additional treatments in both arms will be monitored using a service use interview and LIFE ratings of pharmacological and psychosocial treatments for all mental health contacts, frequency of sessions, length of treatment, and number of days of inpatient and partial hospitalisation. Medication usage and dosing are recorded on a weekly basis as important confounders.

Qualitative Objectives

To understand how participants experience or perceive the intervention to have impacted on their mood, behaviours and symptoms and draw patterns across participants' experiences.

To identify key themes associated with the implementation of CBT_{BAR} from the perspective of key stakeholders

Qualitative Measure/Endpoint

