3. TRIAL DESIGN

The design of the proposed main trial work has been developed with reference to CONSORT (http://www.equator-network.org/reporting-guidelines/consort/) and SPIRIT guidelines (http://www.spirit-statement.org/), and the TIDieR checklist and guide (http://www.bmj.com/content/348/bmj.g1687).

MAIN TRIAL

Our trial will be a multicentre rater-blinded (primary outcome) RCT with 2 parallel arms. It will compare a psychological intervention (CBT_{BAR}) + TAU (treatment condition) to TAU alone (control condition). The trial will recruit 338 participants who meet the Bipolar At Risk (BAR) criteria and randomly allocate them to a 6-month package of either condition.

Randomisation will be independent and concealed, using permuted stratified blocks, where site (5-levels) and BAR group (3-levels) are the stratification factors. It will be conducted via a web-based system conducted within York CTU. Assessors will be masked to allocated treatment. Masking will be maintained using a wide range of strategies (e.g. separate offices for therapists and researchers, protocols for answering phones, message taking and secretarial support, separate diaries and security for electronic randomisation information).

Assessor's blind and independent to treatment group will collect all outcome and mediational variables at baseline, 17-weeks (during treatment window capturing SCID-5 + PSR's (SCID LIFE), HAPPI, BC and ISS), 27-weeks (after therapy cessation), and at 52-weeks. Participants will receive £20 reimbursement upon completion at each assessment point as a thank you for their time.

The assessors will also contact people via phone at 39-weeks to promote retention in the trial. We will ask about general wellbeing since the last assessment (including documenting any potential serious adverse events), and any changes to contact details. Participants will receive a £5 supermarket voucher of their choice to thank them for their continued participation.

For those participants who are randomly selected to receive the CBT_{BAR}, they will be offered up to 26 individual weekly therapy sessions of up to 60 mins in length. These will be delivered by a Clinical Psychologist or psychological therapist.

NESTED QUALITATIVE WORK

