Following the recruitment process, baseline assessment and randomisation, follow-up assessment points will be at 17-, 27-, and 52-weeks post-randomisation (see "Schedule of Events" in the Appendices (#2)). We will also contact people via telephone at 39-weeks to promote retention in the trial and ask about general wellbeing since the last assessment (including documenting any potential serious adverse events, and any changes to contact details). Assessments will be conducted by research assistants blind and independent to treatment group and will employ both a semi-structured interview to gather data for the primary outcome (blinded) and secondary outcomes in addition to self-report questionnaires (unblinded data given the participant will be aware of their treatment allocation). The self-report questionnaires will be offered for completion in paper format.

For those participants who are offered the CBT_{BAR} intervention, a measure of therapeutic alliance (California Psychotherapy Alliance Scales / CALPAS) will be administered to both the participant and the therapist for completion after the 4th and 10th sessions. To ensure the participant is able to complete the measure openly, the trial manager (LP) will be responsible for contacting the participant and arranging administration of this measure to prevent the therapist being the person to do this. Additionally, the Facilitative Alliance Measure will be administered by the trial manager (LP) to the research participants following each follow-up appointment with a research assistant. This will measure alliance with the research assistant.

Follow-up visits are typically offered via face-to-face methods utilising outreach principles where participants are seen in non-stigmatising settings. This approach means that people often choose to be seen at home although other least restrictive venues e.g. youth centres, colleges, primary care settings, are also employed. Staff training will be conducted with all staff and regular arrangements for ensuring inter-reliability across sites. Adapting to assessments via phone/virtual calls still retains validity and reliability on our primary outcome [84].

QUALITATIVE RESEARCH

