The control condition is treatment as usual plus follow-up (17-, 27-, and 52- weeks), which represents an enhancement over routine care since symptoms of mania will be detected earlier than in usual practice and appropriate treatment referrals made. We will not be asking referrers to withhold any treatment. Participation in assessments may reduce the (frequently high) number of contacts required in order to receive appropriate treatment for BD. Assessments will identify untreated BD and any risks to self or others that require immediate action. TAU alone will not include liaison with a clinical team, should one be involved, except where risk issues necessitate this. This is a pragmatic approach that will improve generalisability of our findings. As in previous trials we have undertaken, there will be a clear safety protocol to alert clinicians should suicidal or dangerous ideation emerge, and an operational protocol for initiating high quality routine care should conversion occur.

Treatment as usual will include standard psychiatric care, psychological and vocational interventions from a variety of agencies will be available to both treatment and control arms (although, in our experience, provision for this population is poor). Due to diagnostic uncertainty, access to services includes Improving Access to Psychological Therapies (IAPT), CAMHS, primary care, EIT and community mental health teams. CBT_{BAR} differs from standard NHS treatment for young people with mood swings as highlighted in our RfPB trial [59]. All routine or additional treatments in both conditions will be monitored using a Treatment Documentation Sheet and specific treatments (anti-depressant and psychotherapy treatment) monitored within the LIFE assessment tool as important potential confounders.

CONCOMITANT THERAPY

It would be unethical to restrict the therapeutic options of the young people participating. Our approach will, therefore, be primarily to record the use of all other medication and psychological therapies, document details of dosage, and ensure the follow-up of all randomised participants, irrespective of the interventions that they subsequently receive.

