We will collect participant self-report on the use of medication and psychological therapies (including CBT or CBT informed treatments). All participants will be eligible to receive medications (other than mood stabilisers for longer than 6-weeks or antipsychotics for longer than 3-weeks at baseline) as well as psychological interventions.

ASSESSMENT OF ADHERENCE TO TREATMENT

Four related aspects will be monitored and assessed: (i) participants' adherence to the therapy; (ii) therapist competence (iii) therapist adherence to the manual (iv) overall therapy fidelity. Participants' adherence to the therapy will be assessed by recording the number of sessions offered and attended, including length of sessions attended, and completion of between-sessions tasks (therapy 'homeworks').

Therapist competence and adherence to the manual will be monitored through recordings of therapy sessions, with participants' consent. This is a widely accepted approach to the standardisation of psychological therapies. Therapists will have weekly supervision from a senior clinical psychologist from the central team, who will listen

to and provide detailed feedback on a selection of therapy tapes, with participants' consent, on a weekly basis, to ensure competence and adherence. All therapists and supervisors will also meet remotely with the research team therapy leads for monthly group supervision. This will be done throughout the therapy delivery period to provide quality assurance and ensure action can be taken if required.

Therapy tapes from five participants on each site (total of 25 participants) will be randomly chosen, with participants' consent, to be rated by a clinician independent from the trial, to provide an objective verification of therapist competence and adherence to the manual. Therapist competence will be rated using an existing measure assessing skills and competences related to delivering CBT [93] in line with national programmes and treatment trials utilising CBT models. A rating form for therapist adherence to the manual will be utilised and will consist of a list of therapeutic procedures extracted from the CBT_{BAR} treatment protocol.

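### As written, the blinded rater of the co-primary outcomes also asks about psychological treatment and session frequency, which is likely to reveal allocation for many CBT-arm participants at the week-27 rating

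*Protocol*

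**What the plan says.** **Who rates.** Section 3 (Main Trial): "Assessor's blind and independent to treatment group will collect all outcome and mediational variables at baseline, 17-weeks", and at the later visits. Section 5 (Trial Assessments): "Assessments will be conducted by research assistants blind and independent to treatment group", for the primary and the secondary outcomes.

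**What is rated.** Section 2 defines the primary outcome as "Mood swing symptom severity assessed by SCID-5 + PSR's (SCID LIFE) [1] at 27-week (post treatment"), averaged over the prior four weeks, with one score for depression and one for mania.

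**What else is asked.** Among the additional secondary outcomes at 27 and 52 weeks, section 2 lists: "All additional treatments in both arms will be monitored using a service use interview and LIFE ratings of pharmacological and psychosocial treatments", and these are "for all mental health contacts, frequency of sessions, length of treatment". Section 6 (Control Condition) has "specific treatments (anti-depressant and psychotherapy treatment) monitored within the LIFE assessment tool as important potential confounders". Section 6 (Concomitant Therapy) adds: "We will collect participant self-report on the use of medication and psychological therapies (including CBT or CBT informed treatments").

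**What protects the blind.** Sections 3 and 5 list separate offices and diaries, telephone and message protocols, file security, statements in letters, reminders to clinicians, participants and families, and the timing of qualitative interviews. After a blind break, another assessor is used for later visits where possible. A blinding SOP is promised but is not part of the document.

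**The concern.** The listed measures stop the rater from meeting therapists, seeing files or overhearing messages. None deals with what the rater asks. If the interview that produces the PSR scores also asks how often the participant sees a therapist, the protocol itself carries allocation to the rater.

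PSR is a judgement score, and section 5 calls rater blindness crucial. Participants know their arm, so the self-report measures give no blinded check. A rater who knows or strongly suspects the arm may shift ratings, and both co-primary outcomes would be exposed together. Replacing the assessor afterwards cannot repair a rating made at the visit where the disclosure occurred.

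**Working it through.** **1. Do the questions and the rating meet?**
- Rater: blinded research assistants, for all outcomes (sections 3 and 5).
- Same visit: the service use interview and the LIFE treatment ratings are listed for weeks 27 and 52; the co-primary rating is at week 27 (section 2).
- Same instrument: psychotherapy is monitored within LIFE (section 6), and PSR comes from LIFE (section 2).
- Order of questions: none is stated.
- Exclusion of trial CBT: none is stated.

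That the same person gives the service use interview follows from blinded assessors collecting all outcomes; it is not stated separately.

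**2. How informative would the answers be?** In the feasibility trial 32 of 37 (86%) of the CBT arm had at least 6 sessions (section 6). Assume 1:1 allocation, that trial sessions are reported to the rater, and that a share q of TAU participants report a comparable course. The documents give no value for q. A rater who guesses CBT whenever a course is reported is right with probability (0.86 + 1 − q)/2:

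| q (assumed) | Correct guess |
|---|---|
| 5% | 90.5% |
| 10% | 88% |
| 30% | 78% |
| 50% | 68% |

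Chance is 50%.

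**3. The plan's own sample size.** Inputs from section 3: difference 0.5, SD 1.3, correlation 0.4, two-sided 2.5%, power 90%.
- Residual SD = 1.3 × √(1 − 0.4²) = 1.1915.
- Normal approximation: 2 × (2.241 + 1.282)² × 1.1915² / 0.5² ≈ 141 per arm, 282 in total.
- Noncentral t: 143 per arm, 286 in total, as stated.
- 286/0.85 = 336.5, so 337, or 338 with equal arms, as stated.

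No figure in the plan is in dispute.

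**4. What a rating shift would do.** Depression: SE = 1.1915 × √(2/143) = 0.141. With no true effect and a bias b, the test rejects with probability 1 − Φ(2.241 − b/SE) + Φ(−2.241 − b/SE). Mania: SD 0.5 (section 3) and, as an assumption, the same correlation give SE = 0.5 × √0.84 × √(2/143) = 0.054.

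| Outcome | Assumed bias b | b/SE | Rejection under the null |
|---|---|---|---|
| Depression | 0 | 0 | 2.5% |
| Depression | 0.025 (25% of ratings × 0.1 points) | 0.18 | 2.7% |
| Depression | 0.10 (50% of ratings × 0.2 points) | 0.71 | 6.4% |
| Mania | 0.05 | 0.92 | 9.4% |

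The 0.10 and 0.05 cases are each 20% of the target difference (0.5 and 0.25 points). Neither the shares nor the shifts have a source in the documents.

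**The case against.** **Trial CBT may not be meant.** The monitored treatments are called additional, and the mention of CBT sits under Concomitant Therapy, so the wording may refer to non-trial care. Trial sessions have their own route through adherence data and therapist checklists (section 6). This stands as a possible reading. However, no exclusion is written, the items cover all mental health contacts, and a participant in weekly trial therapy has no stated reason to leave it out.

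**Therapy does not identify the arm.** Psychological interventions are open to TAU participants too. That is why the answer is likely to reveal allocation rather than certain to. The protocol itself calls that provision poor.

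**Safeguards exist.** Participants are reminded about the blind, and an SOP and a Research Assistant Manual are mentioned. The reminders help, but they sit awkwardly beside a direct question on session frequency. The SOP might cover question order. The protocol says it will outline the listed procedures, and none of those is about interview content.

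**Stronger readings that the document does not support.**
- A reader might infer that the rater is already unblinded at week 17. LIFE is given then (section 3), but the treatment items and the service use interview are listed for weeks 27 and 52. The risk exists only if the LIFE treatment section is also given at week 17, which is unclear. If it were, the replacement of assessors would partly address it.
- A reader might infer that PSR is the trial's only blinded measure. YMRS and the SCID mood diagnoses are also rated by interview; the same weakness would reach them.
- A reader might infer a demonstrated inflation of type I error. The shift is assumed, and the milder case is negligible.

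**Conclusion.** The point holds as a gap in the blinding design. As written, the blinded research assistant collects psychosocial-treatment and session-frequency information at the week-27 visit, partly within the instrument that yields the co-primary scores, and no listed measure separates the two. Disclosure is likely for many CBT-arm participants, on the assumption that trial sessions are not excluded from the questions. The size of any resulting bias is unknown: the illustrations for depression run from no practical effect (2.7%) to more than double the nominal error (6.4%). The case for change rests on the structure and the low cost of repair, not on those figures.

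**What to change.** In section 2 (additional secondary outcomes), section 5 (Trial Assessments, Blinding) and section 6 (Control Condition):

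1. Require PSR and the other interview ratings to be completed and locked in REDCap before any treatment or service-use question is put.
2. Take the psychosocial-treatment and service-use items out of the rater's interview. Collect them on a self-completed form returned to the trials unit, or through unblinded staff who do not supervise scoring, and hide these fields from raters.
3. State that anything raters ask about treatment excludes trial sessions, which therapists already record, and that the week-17 LIFE omits the treatment section.

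Locking alone protects the current visit but not the week-52 rating by the same assessor, so steps 1 and 2 belong together.

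The trial manager looks a convenient collector, since that role already gives the alliance measure "to the research participants following each follow-up appointment with a research assistant". But that role knows allocation (section 5) and supervises research assistants on scoring queries (section 10), so it is a poor choice.

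Cost: a change to the assessment order, the form and the SOP, with no new visit and no change in sample size. A self-completed form may give somewhat less complete service-use data than an interview; using unblinded staff instead would take staff time.

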	Conducted in community-based NHS in 5 sites in the UK (representing 4 NHS commissioning regions in England): Greater Manchester, Lancashire, Sheffield, Birmingham, and Norfolk & Suffolk. The research objective is to recruit 338 participants across these 5 NHS sites in England who meet the Bipolar At Risk (BAR) criteria.
Trial Participants	 The study population are young people meeting BAR criteria. The inclusion criteria are: 16-25 years old Meet criteria for one of the following: Group I: Sub-threshold mania:

	 mild depressive symptoms + diagnosis of cyclothymic disorder or bipolar disorder NOS as assessed by SCID-5 Group III: Depression + genetic risk: mild depressive symptoms (Group 1) + genetic risk (first degree relative with bipolar disorder). Help seeking Provision of written informed consent *Please note, the BAR criteria above has been summarised. Please see fully explained criteria in Section 4 / Inclusion Criteria 	
Planned Sample Size	338 participants	
Treatment duration	Up to 26 weeks	
Follow up duration	52-weeks	
Planned Trial Period	April 2022 – March 2026 (48 months)	

	Objectives	Outcome Measures	Timepoint(s) of evaluation of this outcome measure
Primary Outcome	Mood swing symptom severity	SCID-5 assessment + PSR scores (SCID LIFE)	At 27-week timepoint, average over prior 4 weeks
Secondary Outcomes	To determine the impact of the CBT _{BAR} :		
Appraisals of and responses to mood (hypothesised mechanisms)	Proposed mechanism of appraisals of internal state Ascent / descent behaviours	 Internal States Scale (ISS) Hypomanic Positive Predictions Inventory (HAPPI) Behaviours Checklist (BC) 	Baseline, 17- weeks, 27- weeks, & 52- weeks
Mood Swings	On mood swing experiences for the following sub-categories: - 27-week and 52-week FU of time to transition to (hypo)mania - % of time in subthreshold symptoms - Time in symptoms (% of overall time & number of weeks during FU intervals) - Time to recovery from subthreshold (BAR) symptoms	 SCID LIFE (SCID-5 assessment (Modules A, B, C & D) + PSR scores) Young Mania Rating Scale (YMRS) Beck Depression Inventory (BDI) Altman Self Rating Mania Scale 	Baseline, 27- weeks, and 52- weeks

Health Utility	Healthcare costs: Service Use (including health & social care use & informal care)	 Service Use Interview EQ-5D Recovering Quality of Life (ReQoL) 	Baseline, 27- weeks, and 52- weeks

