A qualitative topic guide (after the end of therapy, post 27-weeks will be employed to identify how participants experience or perceive the intervention to have impacted on their mood, behaviours and symptoms and draw patterns across participants' experiences. We will seek to identify components of the intervention that participants continued to utilise beyond therapy, and ways they have incorporated these into their lives.

A qualitative topic guide (after the end of therapy, post 27-weeks) for key stakeholders will be utilised to identify potential barriers and solutions to future implementation.

Hypotheses

Our outcome measures are designed to test the following hypotheses.

Efficacy Hypotheses

- 1) CBT_{BAR} + TAU will lead to improvement in mood swings (SCID-5 + PSR's (SCID LIFE)) compared to TAU alone at
 - a. end of treatment (27-week follow-up)
 - b. follow-up (52-week follow-up).
- 2) CBT_{BAR} + TAU will reduce the likelihood of transition to BD in comparison to TAU alone over a 52-week follow-up time period.

3) CBT_{BAR} + TAU will lead to improved functioning and quality of life compared to TAU alone over a 52week follow-up time period.

Mechanistic Hypotheses

- 1) CBT_{BAR} + TAU will reduce extreme positive and negative appraisals of internal states (HAPPI) and subsequent behaviours used to control mood (BC) at 27 weeks.
- 2) The mechanism by which CBT_{BAR} causes improvement in mood swings (SCID-5 + PSR's (SCID LIFE)) is due to the reduction of extreme positive and negative appraisals of internal states (HAPPI) which in turn improves subsequent behaviours used to control mood (BC) and then internal states (ISS).

Internal Pilot Progression Criteria

An internal pilot will be conducted with a proposed length to month 16 (month 7 of recruitment). By month 16 (γ_3 of the entire recruitment window, month 7 of the recruitment timeline) we plan to recruit γ_3 (68) of our total target (338), see table 1. This will be monitored by the trial management group and reviewed by the Trial Steering Committee as necessary

% / Threshold*	Red	Amber	Green
Trial recruitment	<60% of target (68)	60-99% of target (41-67)	≥100%
	≤40 recruited	41-67	≥68
Recruitment rate/ site/ month	≤1.6	1.6-2.1	≥2.2
Number of sites opened	1-2	3-4	5
Proportion receiving allocated intervention	<90% (≤61)	90-94% (62-64)	≥95% (65)

Table 1. Internal pilot progression criteria at month 16 (month 7 of recruitment window) based upon recruiting 1/5 of total target (threshold = 68*)

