than for mania. On the LIFE PSR, our eligible population will score at the higher end of the subthreshold range (3-4) as those scoring 5-6 will confer research diagnostic criteria and therefore not meet the inclusion criteria for the trial; based on our pilot trial (mean baseline BDI-II score of 37.9), participants will tend to be towards the upper end of the subthreshold range (i.e. mean around 3.75). Button [81] reported that a MCID for the BDI-II is around 17-18%; given that we expected similar sensitivity for the mean LIFE depression PSR scores as would be the case for BDI-II, a difference of around 0.5 points (0.18*[3.75-1]=0.50 (to 2 d.p.)] on the PSR for LIFE depression in order to indicate that CBT_{BAR} is having an important effect.

To detect a between-group mean difference of 0.5 points (SD=1.3 points [80]) on the mean 4-week PSR for LIFE depression score at 27-weeks follow-up we require 286 participants with outcome data to achieve 90% power, using an ANCOVA (with 2.5% two-sided significance level), assuming a conservative correlation of 0.4 between baseline and 27-week scores [82]. Inflating the sample size to allow for a conservative 15% attrition (attrition was 13% in our feasibility trial, 57) requires a target to randomise of 338 participants (approx. 68 per site). This sample size will provide greater than 90% power to detect a rather more conservative MID on LIFE PSR for mania (e.g. equating to 98.5% to detect a target effect of 0.25 points [estimated within-group SD=0.5 points]) [80]. In each case, power will be increased due to the (multiple) correlation between outcome and the full set of explanatory variables adjusted for in the model. We have not allowed for a random therapist effect in our sample size calculation as the effect on depression outcome (BDI-II) in our pilot trial was 0, although the confidence interval was wide; we will, however, include the addition of a random therapist effect amongst our sensitivity analyses.

Assuming a standardised effect size of the intervention on the HAPPI of 0.4, 286 participants with mediator and primary outcome data will also allow for 88.5% power for estimation of an indirect effect of 40% via the putative primary mediator (HAPPI), or 83.5% power for the estimation of a 30% indirect effect, based on a total effect on the intervention of the MCID (i.e. 0.5) (with a 2.5% significance level, estimated using the R package medssp, based functions provided in Vittinghoff and Neilands [83]

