If suspicion of an unacceptable risk, including serious health threat to subjects, arises during the clinical investigation, or when so instructed by the TSC / DMEC or regulatory authorities, the sponsor shall suspend the clinical investigation while the risk is assessed. The sponsor shall terminate the clinical investigation if an unacceptable risk which cannot be controlled is confirmed. The sponsor shall consider terminating or suspending the participation of a particular investigation site or investigator in the clinical investigation if monitoring or auditing identifies serious or repeated deviations on the part of an investigator. If suspension or premature termination occurs, the terminating party shall justify its decision in writing and promptly inform the other parties with whom they are in direct communication. If, for any reason, the sponsor shall inform the responsible regulatory authority as appropriate and ensure that the TSC / DMEC is notified, either by the Chief Investigator or by the sponsor. If the suspension or premature termination was in the interest of safety the sponsor shall inform all other principal investigators.

Access to or breaking the blinding code in the case of suspension or premature termination would be decided by the independent DMEC.

END OF TRIAL

The end of trial is defined by the last visit and completion of data collection of the last participant undergoing the trial, which will be August 2025. The sponsor, or delegated individual in the study team must notify the NIHR and HRA of the end of a clinical trial within 90 days of its completion.

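### Internal pilot Table 1: the Green recruitment rate is about half what 338 participants would need after the pilot, and the receipt criterion counts the TAU arm in its denominator

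*Protocol*

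**What the plan says.** Protocol section 2, Internal Pilot Progression Criteria: "An internal pilot will be conducted with a proposed length to month 16 (month 7 of recruitment"). Table 1 then gives Red, Amber and Green bands for four criteria:

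- Trial recruitment: Red 40 or fewer, Amber 41 to 67, Green 68 or more. The caption describes 68 as one fifth of the total target.
- "Recruitment rate/ site/ month": Red up to 1.6, Amber 1.6 to 2.1, Green 2.2 or more.
- Sites opened: Red 1 to 2, Amber 3 to 4, Green 5.
- "Proportion receiving allocated intervention": Red below 90% (61 or fewer), Amber 90 to 94% (62 to 64), Green 95% or more (65).

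The calendar comes from two other places. The Trial Summary gives the planned period as "April 2022 – March 2026 (48 months"). Section 5, End of Trial, defines the end by "completion of data collection of the last participant undergoing the trial, which will be August 2025". Section 5, Trial Assessments, places the last follow-up 52 weeks after randomisation.

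Section 3, Sample Size, "requires a target to randomise of 338 participants (approx. 68 per site"), built on a "between-group mean difference of 0.5 points (SD=1.3 points [80"]).

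**The concern.** A recruitment-rate criterion should show whether the target is within reach in the time left. Here the Green floor, held constant, leads to a total well short of 338 on the protocol's own dates. The Trial Steering Committee could be shown Green in every row while recruitment runs at about half the rate that the remaining timetable requires.

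The receipt row has a different weakness. Its percentages look like therapy uptake, but its counts fit only a denominator of both arms together. TAU-alone participants have no trial therapy to take up, so including them makes the criterion less sensitive to the problem it would be expected to detect.

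**Working it through.** **Reproducing the plan's own figures.** Inputs from section 3: difference 0.5, SD 1.3, two-sided 2.5%, 90% power, correlation 0.4, attrition 15%.

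- ANCOVA, per arm: 2 × (1.3 × (2.2414 + 1.2816) / 0.5)² × (1 − 0.4²) = 140.95, so 141, or 282 in total. The protocol says "we require 286 participants with outcome data to achieve 90% power".
- 286 / 0.85 = 336.5, so 337, against 338 stated. Both agree closely.
- Pilot target: 338 / 5 = 67.6, so 68. Agrees.

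**Calendar.** Month 1 = April 2022 (assumption from the stated period). Recruitment month 7 = month 16, so recruitment starts in month 10 (January 2023) and the pilot ends in July 2023. August 2025 is month 41. Fifty-two weeks earlier is August 2024, month 29. That leaves 29 − 16 = 13 months after the pilot and a 20-month window. Allowing one extra month gives 14 and 21.

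**Total reached at the Green floor, rate held constant** (5 × 2.2 = 11 per month):

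| Scenario | Total |
|---|---|
| 68 + 11 × 13 | 211 |
| 68 + 11 × 14 | 222 |
| Pilot pace of 68/7 per month for 20 months | 194 |
| 11 per month for all 20 months | 220 |
| 11 per month for all 21 months | 231 |
| Follow-up allowed to run to March 2026 (last randomisation March 2025) | 288 to 297 |

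All are below 338. Only randomising right up to August 2025, which leaves no room for 52-week follow-up, gets there (68 + 11 × 25 = 343).

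**Rate needed after the pilot.** (338 − 68) / (5 × 13) = 4.15 per site per month; with 14 months, 270 / 70 = 3.86. The Green floor is 2.2.

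**Power at 211.** 211 × 0.85 = 179 with outcome data. The residual SD is 1.3 × √0.84 = 1.19, and the standardised distance is 0.5 / (1.19 × √(2/89.7)) = 2.81. Power is 0.708 using the t distribution and 0.715 using the normal approximation. The same formulas give 0.90 at 286.

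**Rate bands against count bands.** Red is cut from Amber at 60% of target by count (41/68), but at 1.6/2.2 = 73% of the Green floor by rate. On the site-months implied by 68 recruits at 2.2 (68/2.2 = 30.9), 41 recruits is 1.33 per site per month and 49 is 1.59. Both are Amber by count and Red by rate; 50 gives 1.62, which is Amber on both. The value 1.6 is also printed in both the Red and the Amber band.

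**Receipt.** 61/68 = 89.7%, 62/68 = 91.2%, 64/68 = 94.1%, 65/68 = 95.6%. The counts match their percentages with a denominator of 68. Section 12 expects 169 of 338 participants to receive CBT_BAR, so about 34 of 68 are in each arm. If all 34 TAU participants count as having received their allocation (assumption):

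- Green, 65: (65 − 34)/34 = 31/34 = 91.2% of the CBT arm.
- Amber floor, 62: 28/34 = 82.4%.
- Top of Red, 61: 27/34 = 79.4%.

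For comparison, section 6 reports that 32 of 37 (86%) in the feasibility CBT arm had at least 6 sessions and that all had at least 1. Pooled with a full TAU arm, 86% becomes (34 + 34 × 32/37)/68 = 93%, which is Amber. On the CBT arm alone against the same 90% limit it would be Red.

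**The case against.** A reader might infer that any trial rated Green would fall short, or that 338 cannot be reached. The documents do not support that. Both Green thresholds are open-ended minimums. One fifth of the target by month 7 of a window of about 20 to 21 months already implies faster recruitment later. The 211 describes a trial sitting exactly on the floor whose rate never rises, and the 71% power rests on the same condition. The calendar is also inferred, not stated. Table 1 is not an automatic gate either: the trial management group monitors it, the Trial Steering Committee reviews it as needed, and both that committee and the DMEC follow recruitment throughout. All of this stands, and it limits the point to the threshold itself: the implied acceleration is not stated anywhere and no criterion tests it.

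A reader might also divide 68 and 41 by 5 sites × 7 months, get 1.94 and 1.17, and conclude that the two recruitment rows contradict each other outright. That assumes all five sites open from the first day, whereas the table has its own row for sites opened, which anticipates staggered opening. On about 31 site-months, 68 does correspond to 2.2. What survives is narrower: the two rows scale their lower bands differently, and 1.6 appears twice.

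On receipt, the row is labelled by allocated intervention, does not claim to measure therapy uptake, and leaves receipt undefined. Nor would a marked uptake problem score Green: Green still needs about 91% of the CBT arm, more than the feasibility trial's 86% for at least 6 sessions. The dilution is real but moderate, and its exact size depends on how TAU receipt is counted.

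**Conclusion.** The point holds in this limited form. The Green rate of 2.2 is a little over half of the 3.9 to 4.2 per site per month needed after a pilot that has just met its target. The shortfall at the floor remains on every calendar examined that leaves room for 52-week follow-up, although its size varies. The figures rest on month 1 being April 2022, on randomisation closing about August 2024, and on a constant rate at five sites.

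The receipt percentages do not describe uptake in the CBT arm. That conclusion rests on about 1:1 allocation within the pilot and on TAU participants counting as having received their allocation; the pooled denominator itself follows directly from the table.

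This should be fixed because the thresholds inform the progression decision. It is not more serious than that: the primary analysis and the stated sample size are unaffected.

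**What to change.** 1. Set the Green rate as (338 − number recruited) / (5 × months left), about 3.9 to 4.2 if 68 are recruited, and judge it on the last pilot months per open site. Alternatively, restate the recruitment and end-of-trial dates so that the intended rate delivers 338.
2. Scale the Amber and Red rate bands from that Green value with the same 60% cut as the count row, and let 1.6, or whatever replaces it, belong to one band only.
3. Compute the receipt criterion on the CBT arm alone (about 34 participants). Define receipt first and set the cut-offs to match. The choice matters: the feasibility trial's 86% (at least 6 sessions) would be Red against the present 90% limit, while its 100% (at least 1 session) would be Green.

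The cost is a revised Table 1 and possibly a revised date. The downside is that the pilot becomes harder to pass, and a percentage based on about 34 participants moves by roughly 3 points per person (1/34).
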